3.3. Sample size

The sample size for this pilot is based on the confidence interval approach recommended by Cocks and Torgerson for pilot clinical trials.²⁹ For the definitive trial, the planned sample size is 190 (95 participants on active drug, 95 on placebo), to provide 90% power to detect a difference of 2.8 in the changes in ACT score from baseline to 24 weeks for the roflumilast versus placebo, with a type 1 error rate of 5%, and a standard deviation (SD) of 5. The SD is based on prior data from studies by our research network, and previous publications.^{30,31} A pilot study of 28 to 34 participants provides 90% one-sided confidence limit to exclude a clinical important effect in a definitive trial if we see no effect in the pilot study, and so could inform the decision as to whether to proceed to the full definitive trial. We will inflate this to 38 participants to allow for possible loss to follow up.

Table: Recommended pilot sample size for continuous outcome measures*

Standardized effect size for main trial	Pilot Sample size (90% level)	Upper 90% one-sided confidence limit
0.5	28	0.4844
0.45	34	0.4397
0.4	42	0.3955
0.35	54	0.3488
0.3	74	0.298

* Adapted from Cocks & Torgerson (2013)²⁹

3.4. Data confidentiality

Data which includes identifiable personal health information (PHI) are collected at each of the clinical sites. PHI is stored at each of the clinical sites in accordance with HIPAA regulations and local university and hospital policies. This includes the storage of PHI in locked cabinets or rooms, limited access to secure data areas by certified participating study personnel, password protection for electronic medical records, and explanation of HIPAA regulations on the study consent form. Data such as lung function or laboratory tests that are collected as part of this study may be transmitted to the participants treating physicians with the consent of the participant. Participants are informed in the consent that PHI may also be disclosed for auditing purposes by the FDA or other regulatory bodies and is subject to subpoena.

Information transmitted to the coordinating center is identified by an anonymous study ID, and other identifying information such as birthdate, visit dates, and study site is removed from limited use datasets. Source records that are transmitted to the coordinating center for data quality audits have identifying information redacted.

4. Human subjects

4.1. Risks of Individual Procedures

4.1.1. Roflumilast

Roflumilast will be provided to 19 subjects for 24 weeks at the 7 centers. While roflumilast has been approved for use in patients with COPD, the label includes warnings about psychiatric events (including suicidality), weight loss, and drug interactions. The psychiatric adverse reactions included insomnia, anxiety and depression (rate of psychiatric adverse reactions was 2.6% higher in roflumilast group than placebo). Instances of suicidal ideation and behavior, including completed suicides, were observed in clinical trials and in the post-marketing surveillance of the drug, in individuals with and without any prior history of depression. Of note, the safety data for roflumilast were based on 4438 patients between the ages of 40-91 years, 73% of whom were male and 92.9% were Caucasian. Given these limitations (in comparison to the planned trial in patients with asthma), the safety risks are taken from a pooled analysis of asthma patients receiving the 500 mcg dose of roflumilast to be used in the current trial (n=1567; Chervinsky, P et al Pulmonary Pharmacology and Therapeutics 2015 (35):S28-34). (This asthma population was 42.2% male, 80.2% white, and had a mean BMI of 27.47 as well as including 96.7 % of subjects between the ages of 12-65 years. Treatment duration varied between 4-24 weeks.) In these studies of patients with asthma, the risks that occurred with more than 5 events per 100 patient years follow up in excess of the control group included:

Excess incidence rate of adverse events for roflumilast compared to placebo by System Organ Class (SOC)*:

- Gastrointestinal disorders (61.7 cases per 100 patient years)
 - Diarrhea (21.0 cases per 100 patient years)
 - Nausea (24.0 cases per 100 patient years)
- Psychiatric disorders (7.1 cases per 100 patient years)
 - Insomnia (6.0 cases per 100 patient year)
- Nervous system disorders (33.7 cases per 100 patient years)
 - Headache (20.8 cases per 100 patient year)
 - Dizziness (6.2 cases per 100 patient years)
- Musculoskeletal and connective tissue (19.8 cases per 100 patient years)
- Infections and infestations (19.2 cases per 100 patient years)

*Includes SOCs and the associated preferred terms for events with an excess of >5.0 cases per 100 patient years for the difference between roflumilast and placebo where 95% confidence interval does not include 0.

Anticipated % patients experiencing an event compared to placebo if treated for 24 weeks with roflumilast 500 mcg per day (based on data above):

- diarrhea (9.7%)
- nausea (11.1%)
- insomnia (2.8%)
- headache (9.6%)
- dizziness (2.9%)

The psychiatric risks of roflumilast treatment are mitigated through the monitoring and management of symptoms as described below.

Weight loss is considered to be an advantageous outcome in the population being studied. *If a participant loses ≥ 10% of baseline weight during the course of the trial, this will be discussed with the study physician (preferably the study PI) as soon as possible.*

The GSRS will be used primarily to monitor GI side-effects, if a participant scores ≥ 6 on any item (indicative of severe or very severe discomfort), this will be discussed with the study doctor immediately, and the study PI as soon as possible.

The potential for drug interactions with roflumilast is mitigated through excluding participants on medications known to interact with roflumilast. We will exclude participants with uncontrolled anxiety and depression, and suicidal ideation, and screen for these at every visit, we will discontinue the patient from drug treatment if they develop these symptoms (threshold as defined in eligibility criteria). Plans for dealing with elevated symptoms of depression, anxiety and self-harm are outlined below.

4.1.2. Venipuncture

The main risk of this is bruising and minor discomfort. We may find elevated fasting blood glucose, which requires clinical follow up. Our plan is as follows:

< 100: no action

100-125: notify participant and PCP within 3 months

126-199: notify participant and PCP within 5 working days

200-299: notify participant and PCP within 24 hours

≥ 300: contact participant immediately, and advise to go to PCP/ ED/ urgent care

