2.1.2. Exclusion criteria

- Participation in an investigational study within the past 4 weeks
- Physician diagnosis of chronic obstructive pulmonary disease
- Any condition that puts the participant at risk from weight loss as judged by the site physician
- Liver cirrhosis
- Major psychiatric disorders such as generalized anxiety disorder, major depressive disorder, history of suicidal ideation/ attempt, panic disorder, post-traumatic stress disorder, schizophrenia, schizoaffective, substance abuse or other disorders that in the opinion of the study physician that would affect study participation
- > 0 time use of illicit drugs in the past 12 months
- > 0 time use of cannabis in the past 12 months
- Uncontrolled depression as defined by a score of 15 or greater on the depression questions of the PHQ-9
- Suicidal ideation (a score of greater than 0 on Question 9 on the PHQ-9)
- Uncontrolled anxiety as defined by a score of 10 or greater on the anxiety questions of the GAD-7
- Pregnancy/lactation
- Females of childbearing age who do not agree to practice an adequate birth control method (abstinence, combination barrier and spermicide, or hormonal) for the duration of the study.
- Greater than 20 pack year smoking history, or smoking within the last 6 months.
- History of bariatric surgery
- Drugs metabolized by cytochrome P450 (rifampicin, phenobarbital, carbamazepine, phenytoin, erythromycin, ketoconazole, cimetidine, fluvoxamine, enoxacin, oral contraceptives containing ethinyl estradiol with gestodene).
- Currently on roflumilast or theophylline (patient may wash out of these medications for 4 weeks prior to visit 1).
- Intention to move out of area within the next 6 months

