2.9. Procedures

Sites conducting remote follow up visits must use a secure (password protected) zoom link or other secure online communication method. Participants who are followed up remotely, will complete some questionnaires over the phone and mail back the rest of the questionnaires to the site.

Outline of Study Visits							
Week	-1	0	2	6	12	18	24
Visit number	V1	V2	V3	V4	V5	V6	V7
Consent	•						
Baseline/interim history	•	•	•	•	•	•	•
Randomization		•					
Pill distribution†		•		•	•		
Pill distribution‡		•			•		
Review of paper/electronic diary cards		•	•	•	•	•	•
Pill Counts			•	•	•	•	•
Asthma Control	•	•	•	•	•	•	•
Anxiety/depression questionnaires	•	•	•	•	•	•	•
GSRS	•	•	•	•	•	•	•
QOL	•	•	•	•	•	•	•
Anthropometrics	•	•	•	•	•	•	•
Fasting Blood draw¥		•					•
Pregnancy test*	•	•	•	•	•	•	•
End of study questionnaire							•

† if dose frequency is every day since V3

‡ if dose frequency is every other day since V3

¥ conduct blood draw only if site permits it

*for women of child-bearing potential and participating in remote follow up participants will be mailed testing kit, and asked to send photo of result to coordinator

- Participants will be trained on how to perform peak expiratory flow at the study visit and sent home with asthma action plan.
- Asthma paper/electronic diary cards will be completed by participants throughout the study to record daily morning peak expiratory flow (PEF), daily asthma symptom scores, beta-agonist use, nocturnal asthma awakenings, and health care use.^{17,18} Diary data are used to identify episodes of poor asthma control and days with no asthma symptoms (asthma-free days).
- The Asthma Control Test (ACT) is a 4-week recall questionnaire that measures asthma control.¹⁹
- The Marks Asthma Quality of Life Questionnaire (Marks AQLQ) assesses asthma specific quality of life.²⁰
- The Asthma Symptom Utility Index (ASUI) is a 2-week utility-weighted asthma symptom questionnaire.²¹
- GI side effects will be assessed with the Gastrointestinal Symptom Rating Scale. This is a 15-item instrument with five subscales (reflux, diarrhea, constipation, abdominal pain and indigestion) that was originally developed to assess the symptoms associated with the most common GI disorders, and has previously been used to assess tolerability of medications. The five subscales of the questionnaire produce a mean score ranging from 1 (no discomfort) to 7 (very severe discomfort).²²

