- Medical Outcomes Study (SF36) is a measure of general health related quality of life which correlates with asthma outcomes.^{23,24}

- The Patient Health Questionnaire for Depression and Anxiety (PHQ9 and GAD7) will be used. The Patient Health Questionnaire is a diagnostic tool for mental health disorders used by health care professionals that is quick and easy for patients to complete. We have used this questionnaire in prior ALA-ACRC studies, and so the centers are familiar with its use. We will use sections specific to mood (PHQ-9) and anxiety (GAD-7). The PHQ-9, a tool specific to depression, scores each of the 9 DSM-IV criteria based on the mood module from the original PRIME-MD. The GAD-7 was subsequently developed as a brief scale for anxiety and scores seven common anxiety symptoms.^{25,26}
- Anthropometrics will include blood pressure, height and weight, and waist and hip circumference per NHANES III.²⁷ Digital scales will be given to participants at visit 2 to take home to measure weight. Participants will be asked to send a photo of the weight shown on the scale along with their feet to the coordinator.
- Adverse effects will be assessed by open-ended questions at each visit and rated in severity.
- Interval health history will be recorded at each clinic visit. Records of all hospitalizations and, if necessary, deaths are obtained for verification of diagnoses and assessment of safety issues.
- Baseline questionnaires and exam will be administered to ascertain demographics including self-reported ethnicity and race, general health, co-morbid conditions, asthma symptoms, and medication use.
- Assessment of Adherence: adherence will be assessed from pill counts when participant returns pills at each study visit after randomization. If only remote visits are permitted, then pill count will be completed when participant mails back drug bottles at the end of the study.
- Exit questionnaires will be administered at the last visit to determine global assessments of treatment, adequacy of informed consent procedures, satisfaction with study procedures and personnel, and opinions about the intervention.
- Blood specimens will be collected for fasting blood glucose and analysis of metabolic and oxidative markers related to asthma if a site permits this. Excess blood specimens will be used for future asthma research with the patient's consent. Fasting blood draw may take place within 7 days of rest of the procedures scheduled for visit 2 or visit 7.

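### The fasting-glucose action table sends every result below 100 to no action, with no lower limit, so a clinically low value prompts no notification

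*Combined protocol and SAP*

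**What the plan says.** Section 4.1.2 (Venipuncture) introduces the action list with "We may find elevated fasting blood glucose, which requires clinical follow up. Our plan is as follows". Five bands follow, with no unit. The lowest is "< 100: no action". The other four (100-125, 126-199, 200-299, and 300 or more) call for increasingly urgent contact, from notice to the participant and PCP within 3 months up to immediate contact and referral for care.

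The visit table in section 2.9 schedules fasting draws at visit 2 (week 0) and visit 7 (week 24), with the footnote "conduct blood draw only if site permits it". The draw may fall within 7 days of the visit's other procedures.

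The eligibility criteria (sections 2.1.1 and 2.1.2) neither mention diabetes nor exclude glucose-lowering drugs as such. The nearest exclusion is "Any condition that puts the participant at risk from weight loss as judged by the site physician".

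**The concern.** The list is meant for high values, but it does not stop there. It includes a row for values that are not elevated and gives one instruction for all of them. Silence on low values would have left them to clinical judgement; a written no-action rule tells staff that nothing is required. A site following the table literally need not tell the participant or the PCP about a clinically low fasting result that the study already holds.

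The result also sits oddly with the protocol's own standard: a value of 105 leads to notification within 3 months, while a value of 45 leads to nothing.

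What is at stake is individual participant safety. The treatment comparison is not affected.

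**Working it through.** The plan gives no figure to reproduce here. The check has three parts: the coverage of the bands, a search for any other rule, and a count of the results exposed.

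**1. Coverage of the bands (section 4.1.2)**

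| Fasting glucose (unit not stated; mg/dL assumed) | Action, paraphrased |
|---|---|
| below 100, no floor | none |
| 100-125 | tell participant and PCP within 3 months |
| 126-199 | tell both within 5 working days |
| 200-299 | tell both within 24 hours |
| 300 or more | contact at once and direct to care |

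Every whole-number value has a row. Any low value, for example 45 (illustrative), falls in the first.

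**2. Other provisions that might cover a low result**

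- Section 2.9: "Adverse effects will be assessed by open-ended questions at each visit and rated in severity". Interval health history is also taken at clinic visits. Both can find a symptomatic episode; neither is triggered by a laboratory value.
- Section 3.4: laboratory results may go to treating physicians with the participant's consent. This is permissive and sets no threshold or deadline.
- Section 5: a medical monitor reviews reports of serious adverse events and unusual events. Someone must first file a report.
- Section 2.1.2: the weight-loss exclusion could remove some users of glucose-lowering drugs, but not all.

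None of these is a rule for a low glucose value. Cover is thinnest at visit 7. It is the last scheduled visit, and because the draw may fall up to 7 days from the other procedures, a result can arrive after the last planned questioning.

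The front matter before section 1.1 and section 5.1 were not in the text available. The change log titles section 5.1 as the composition of the DSMB, so a glucose rule there is unlikely.

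**3. Number of results exposed**

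Inputs: 38 participants (section 3.3); 19 on roflumilast (section 4.1.1: "Roflumilast will be provided to 19 subjects for 24 weeks at the 7 centers"); two scheduled draws each (section 2.9).

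- Maximum results: 38 + 38 = 76.
- Visit 7 results on roflumilast: 38 / 2 = 19, which is 19 / 76 = 25%. The placebo arm has the same number.
- Section 3.3 gives a pilot size of 28 to 34 and then says "We will inflate this to 38 participants to allow for possible loss to follow up". If losses use up that allowance, 4 to 10 participants are lost (4/38 = 10.5% to 10/38 = 26.3%).
- Total results would then be 38 + 28 = 66 to 38 + 34 = 72.
- Visit 7 results on roflumilast would be 28 / 2 = 14 to 34 / 2 = 17, assuming equal loss by arm.

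These are counts of draws, not of low values. They bound the exposure from above and fall further where sites do not permit draws.

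**The case against.** The strongest reply is about scope. The list opens with "We may find elevated fasting blood glucose, which requires clinical follow up", so its bottom row most naturally means that no follow-up for elevation is needed. On that reading it is the reference row of a high-glucose plan, and no sensible clinician would take it as an order to ignore a value of 45. Sections 3.4 and 5 also give routes by which a low result could reach a treating physician or the medical monitor.

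Nor is a hazard from the drug shown. Section 4.1.1 lists the adverse events in excess on roflumilast, and hypoglycaemia is not among them. The draw counts do not measure how often a low value would occur, and the 28 to 34 range is a sample-size recommendation, not a retention forecast.

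Much of this stands. The point is a gap in the safety plan, not an internal contradiction. It rests on participants who may happen to run low, not on a shown drug effect, and its frequency is unknown. What does not stand is that the other provisions close the gap: they are permissive, or they depend on symptoms or a filed report. The table's purpose explains how the row came to be written that way, but the row still gives an explicit instruction that is wrong for a low value.

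**Conclusion.** The concern holds as a minor safety correction. The no-action row has no floor, and no other rule for a low fasting glucose was found in the text available. Exposure is at most 76 results, of which at most 19 are on-treatment roflumilast results at visit 7; under the planned loss allowance it is 66 to 72, with 14 to 17. The number of low results cannot be derived from the documents and could be zero.

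This rests on reading the unit as mg/dL, on equal loss by arm for the reduced counts, and on the sections not available containing no such rule. Confidence is high that the floor is missing. No claim is made about how often it would matter. The primary outcome, its analysis and the decision on a definitive trial are untouched.

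**What to change.** In section 4.1.2:

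- State the unit.
- Limit the no-action row to values from a clinician-set floor up to 99.
- Add one row for values below the floor that requires prompt contact with the participant and PCP.

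A floor of 70 mg/dL is an example only and is my assumption. The study physicians and the DSMB should set both the floor and the deadline for contact. Automatic recording as an adverse event is not needed.

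The cost is one row edited and one added, with no new test, visit or staff. The downside is an occasional extra notification.

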4.2. Handling elevated symptoms: Depression, anxiety, and self-harm

This proposed plan will be subject to DSMB review.

We will ask all patients if they have a mental health care provider at the beginning of the study.

The questionnaires used in this study include questions regarding the participant's health - both physical and mental. If a participant is experiencing a mental health crisis, we will provide them with additional support and referrals as needed. Information provided will include the following:-

- The National Strategy for Suicide Prevention, [name] 24 hour hotline
- Howard Center [name] [contact] local Crisis 24 hour hotline
- Seneca Center [name] [contact]
- Northeastern Family Institute [name] [contact]
- UVMMC Psychiatry: [name] [contact]

In addition, each site will identify a psychiatrist or licensed psychologist to be available to discuss any issues related to depression/anxiety with the PI.

4.2.1. Protocol for participant with elevated depression and anxiety symptoms

The PHQ-9/ GAD-7 captures the presence and severity of depression and anxiety symptoms. Scores above the specified thresholds suggest a clinically significant level of psychological distress. It does not necessarily mean that the participant has a clinical diagnosis of depression or anxiety but may indicate the need for appropriate care. **Study personnel will be instructed to tabulate and review the scores for these instruments before the participant is released from the study visit.**

Participants with scores on the PHQ-9 or GAD-7 (including those being screened for the eligibility who do not qualify for the study) that reach or exceed the thresholds for exclusion outlined in the study eligibility criteria will be discontinued from study drug under the supervision of the site PI (if on study drug), and the site PI will ensure that the site specific plan for managing these participants is instituted. Participants already randomized into the study will continue to be followed for the rest of the study off of study drug (unless they decide to withdraw). Subsequent scores exceeding the threshold score, or the minimally clinically important difference for the questionnaires when compared to Visit 2 (≥ 5) will be considered an adverse event, and, as such, followed until resolution or a plan for care under the supervision of another medical provider is established. This will be considered an adverse event, and, as such, followed until resolution or a plan for care under the supervision of another medical provider is established. Participants will be informed that the elevated score could be related to the study drug, though investigators and subjects will not be unblinded to treatment assignment.

4.2.1.1. Elevated depression scores

Elevated depression scores are defined as:

- Total score of 15 or greater on the depression questions of the PHQ-9 or an increase of 5 points or more from score at Visit 2.

If depression score is elevated, we will tell the participant the following:

- *"It seems that you are "down" or somewhat distressed. I would like to give you a few names and numbers of people in the community you can contact for assistance." OR "Your score is a bit high. Are you feeling "down" or upset? Would you like to have some names and numbers to contact for help?"*
- Offer patient the mental health resource information
- We will follow up with participants who have elevated depression by phone within 7 days to check on follow up with mental health care resources, or mail them a letter with resources if we are unable to reach them by [contact]. Elevated anxiety scores

Elevated anxiety scores are defined as:

- Total score of 10 or greater on the anxiety questions of the GAD-7 or an increase of 5 points or more from score at Visit 2.

If anxiety score is elevated, we will tell the participant the following:

- *"It seems that your anxiety may be causing you a lot of stress. I would like to give you a few names and numbers of people in the community you can contact for assistance." OR "Your score is a bit high. Are you feeling anxious or 'on edge' a lot? Would you like to have some names and numbers to contact for help?"*
- Offer patient the mental health resource information
- We will follow up with participants who have elevated anxiety scores by phone within 7 days to check on follow up with mental health care resources, or mail them a letter with resources if we are unable to reach them by phone.

